2. ANALYSIS OBJECTIVES

- To evaluate the efficacy of VM202 in promoting ulcer healing in nonhealing foot ulcers
- To evaluate the safety of intramuscular administration of VM202 in subjects with nonhealing foot ulcers

3. STUDY DESIGN

This is a phase III, randomized, double-blind, placebo-controlled, multicenter, 7-month study designed to assess the safety and efficacy of intramuscular injections of VM202 in the calf of diabetic patients with chronic nonhealing foot ulcers and concomitant PAD. Subjects with confirmed PAD and diabetes aged \geq 18 years to \leq 80 years diagnosed with nonhealing foot ulcers will be screened for study eligibility after giving informed consent.

At Screening, standard of care will be initiated that will continue for the duration of the study, as follows:

- Surgical debridement of necrotic tissue or devitalized tissue
- Use of appropriate off-loading when ambulating
- Maintenance of moist wound environment

Three hundred patients (from up to 30 study centers) who meet the eligibility criteria will be randomized in a 2:1 ratio to one of two treatment groups: 200 patients with VM202 (16 mg) plus standard of care or 100 subjects with placebo plus standard of care, respectively. Safety will be monitored throughout the study by an independent Data Safety Monitoring Board (DSMB, Section 8.5).

Patients will receive intramuscular injections in the ipsilateral calf of the affected foot with the target ulcer of either VM202 or placebo on Day 0, Day 14, Day 28, and Day 42 as follows:

Treatment: Days 0, 14, 28, and 42

TREATMENT]	DOSE VM20	FINAL DOSE		
GROUP	DAY 0	DAY 14	DAY 28	DAY 42	VM202 (mg)
VM202	4	4	4	4	16
Placebo	0	0	0	0	0

0 indicates injections of Placebo

VM202 will be delivered in a solution of 0.5 mg VM202 / mL. All subjects will receive sixteen (16) 0.5-mL intramuscular injections of VM202 or placebo at each injection visit.

The schedule of study visits and the clinical parameters that will be measured at the visits are summarized in Table 1 to Table 3 below.

The subjects' target ulcer will be evaluated by photograph, surface area, depth, perimeter and volume measurements. Subjects must have a non-healing ulcer on Day 0 that meets study entry inclusion criterion # 5 and does not meet exclusion criterion #6 to be eligible for study participation. Subjects will continue to come to the clinic once a week for dressing changes and wound assessment until the ulcer has healed or study exit, whichever comes first. Measurement of the target ulcer will be performed at each follow-up visit until complete wound closure or study exit.

Further details on the study procedures and conduct are provided in the protocol.

Table 1 Schedule of Evaluations: Baseline through All Study Injections

	Table 1	Wound	1 st Inj	ection	2 nd Inj	ection	3 rd In	jection	4 th In	jection	Confirmation of	
	Screening /	Assessments	Da	y 0	Day 14	1 ± 3 D	Day 2	8 ± 3 D	Day 4	2 ± 3 D	Ulcer Healing	
Procedure	Baseline (-45 D to	& Dressing Changes -	Pre-	Post-	Pre-	Post-	Pre-	Post-	Pre-	Post-	(14D ± 5D after visit in which	Early Withdrawal
	-7 D)	Weekly††	dose	dose	dose	dose	dose	dose	dose	dose	ulcer was not	Withdrawar
		, , , , , , , , , , , , , , , , , , ,	Gose	uose	aose	uose	uose	Gose	GOSE	dose	measurable)	
Baseline Evaluation												
Informed Consent	✓											
Medical History	✓											
Physical Exam	✓											
Cancer screening [†]	✓											
Viral screening – HIV, HTLV, HBV, HCV	✓											
Foot x-ray	✓											
Retinal Fundoscopy	✓											
EKG	✓											
Urine Pregnancy test (women of childbearing potential only)	✓											
Safety and Efficacy Parameters												
Vital Signs	✓	√ *	✓	✓	✓	✓	✓	✓	✓	✓	√ ∗	✓
Concomitant Medications	✓	✓	✓		✓		✓		✓		✓	✓
Photograph and measurement of ulcer in target leg	✓	✓	✓		✓		✓		✓		✓	✓
Serum Chemistry and hematology	✓		✓						✓			✓
ABI & TBI	✓		✓									
Toe pressure	✓											
TcPO ₂			✓									
CWIQ			✓									
HbA1c	✓		✓									
Study Injections			✓		✓		✓		✓			
Copies of VM202 in whole blood			✓	√ **	✓	√ **	✓	√ **	✓	√ **		√1
Serum HGF			✓				✓					√1
Treatment												
Injection site reaction assessment		√3		✓	✓	✓	✓	✓	✓	✓	√3	√2
Adverse Events		✓		✓	✓	✓	✓	√ -ti(1.11	✓	✓	✓	✓

[†] Cancer screening: see Protocol Section 4.1.3

- If withdrawal occurred before Day 90 Visit
- 2 If withdrawal occurred before Day 60 Visit
- 3 If visit occurs after first injection visit and before Day60

^{††} Ulcer assessment and dressing changes to be conducted once weekly. Confirmation of ulcer healing to be conducted 2 weeks (± 5 days) after visit in which ulcer is not measurable

^{*} Excluding weight

^{** 2} hours after injection (± 1 hour)

Table 2 Schedule of Evaluations: Post Study Injections through Study Completion

PROCEDURE PROCEDURE	Wound Assessments & Dressing Changes - Weekly††	Day 60 ± 3 D	Day 74 ± 3 D	Day 90 ± 7 D	Day 120 ± 7 D		Confirmation of Ulcer Healing (14D ± 5D after visit in which ulcer was not	Early Withdrawal
	***						measurable)	
Baseline Evaluation								
Informed Consent								
Medical History								
Physical Exam								
Cancer screening [†]								
Viral screening – HIV, HTLV, HBV, HCV								
Foot x-ray								
Retinal Fundoscopy						✓		
EKG								
Urine Pregnancy test (women of childbearing								
potential only)								
Safety and Efficacy Parameters								
Vital Signs	√ *	✓	✓	✓	✓	✓	√ *	✓
Concomitant Medications	✓	✓	✓	✓	✓	✓	✓	✓
Photograph and measurement of ulcer in target leg	✓	✓	✓	✓	✓	✓	✓	✓
Serum Chemistry and hematology				✓	✓	✓		✓
ABI & TBI					✓	✓		
TcPO ₂								
CWIQ					✓	✓		
HbA1c					✓	✓		
Study Injections								
Copies of VM202 in whole blood		✓		✓				√1
Serum HGF		✓		✓				√1
Treatment								
Injection site reaction assessment	√3	✓					√3	✓2
Adverse Events	✓	✓	✓	✓	✓	✓	✓	✓

^{††} Ulcer assessment and dressing changes to be conducted once weekly. Confirmation of ulcer healing to be conducted 2 weeks (± 5 days) after visit in which ulcer is not measurable

^{** 2} hours after injection (± 1 hour)

^{*} Excluding weight

¹ If withdrawal occurred before Day 90 Visit

² If withdrawal occurred before Day 60 Visit

³ If visit occurs after first injection visit and before Day 60

Table 3 Schedule of Laboratory Evaluation

Parameters	Screen	Day 0	Day 14	Day 28	Day 42	Day 60	Day 74	Day 90	Day 120	Day 210	Early Withdrawal
Visit Number	1	2	3	4	5	6	7	8	9	10	
HbA1c	✓	✓							✓	✓	
Serum HGF		✓ pre- injection		✓ pre- injection		✓		√			√ 1
VM202		✓ pre & post injection	✓ pre & post injection	✓ pre & post injection	✓ pre & post injection	✓		✓			√ 1
HTLV, HIV-1, HIV-2	✓										
Hepatitis B, Hepatitis C [†]	✓										
Hematocrit	✓	✓			✓			✓	✓	✓	✓
Hemoglobin	✓	✓			✓			✓	✓	✓	✓
RBC	✓	✓			✓			✓	✓	✓	✓
WBC with differential	✓	✓			✓			✓	✓	✓	✓
Platelets	✓	✓			✓			✓	✓	✓	✓
Albumin	✓	✓			✓			✓	✓	✓	✓
Alkaline Phosphatase	✓	✓			✓			✓	✓	✓	✓
ALT	✓	✓			✓			✓	✓	✓	✓
AST	✓	✓			✓			✓	✓	✓	✓
Bicarbonate	✓	✓			✓			✓	✓	✓	✓
BUN	✓	✓			✓			✓	✓	✓	✓
Calcium	✓	✓			✓			✓	✓	✓	✓
Chloride	✓	✓			✓			✓	✓	✓	✓
Creatinine	✓	✓			✓			✓	✓	✓	✓
eGFR	✓										
Glucose	✓	✓			✓			✓	✓	✓	✓
Potassium	✓	✓			✓			✓	✓	✓	✓
Sodium	✓	✓			✓			✓	✓	✓	✓
Total Protein	✓	✓			✓			✓	✓	✓	✓
Total Bilirubin	✓ · · · · · · · · · · · · · · · · · · ·	√ (1. M. III)	A1\\ 21 1 4	II .''' D . C	√ (IID 41)	TT 4'4'	D (√ (III)	√ 177	√ · · · · · · ·	√ (A €

Hepatitis B core antibody (IgG and IgM; HBcAb), antibody to Hepatitis B surface antigen (HBsAb), Hepatitis B surface antigen (HBsAg) and Hepatitis C antibodies (Anti-HCV)

If withdrawal occurs before Day 90 Visit

4. STUDY ENDPOINTS

4.1. Primary Efficacy Endpoint

The primary efficacy endpoint is the proportion of subjects with a target wound closure by the 4-month follow-up.

The statistical hypotheses for the primary efficacy endpoint are:

 H_0 : $P_t = P_c$ versus H_a : $P_t \neq P_c$

where P_t and P_c are the proportions of subjects with a target wound closure by the 4-month follow-up for the VM202 and placebo groups, respectively.

The hypothesis testing will be at a two-sided alpha of 0.05.

4.2. Other Efficacy Endpoints

- Time to complete wound closure of foot ulcer
- Proportion of subjects with a target wound closure by 7 months
- Percent change in wound volume at 2 months (Day 60), 2.5 months (Day 74), 3 months (Day 90), 4 months (Day 120), and 7 months (Day 210)
- Percent change in wound perimeter, area and wound depth at 2 months, 2.5 months, 3 months, 4 months, and 7 months
- Proportion of subjects with formation of new ulcers on the target foot by 2 months, 2.5 months, 3 months, 4 months, and 7 months
- Time to major amputation in the target limb
- Time to minor amputation in the target limb
- Change in target limb ABI at 4 months and 7 months
- Change in target limb TBI at 4 months and 7 months
- Change in TcPO₂ at 4 months and 7 months
- Change in the overall quality of life and each domain score (well-being, physical symptoms and daily living, social life) of CWIQ from Day 0 at 4 months and 7 months

4.3. Safety Outcomes

- Adverse events
- Injection site adverse events

- Vital signs
 - o Blood pressure
 - Weight
 - Heart rate
 - o Respiration Rate
 - o Temperature
- HbA1c
- Serum Chemistry and Hematology
- Retinal fundoscopy

4.4. Pharmacokinetics

- HGF serum levels
- Number of copies of VM202 in whole blood

4.5. Planned Covariates

The primary efficacy endpoint will be analyzed by adjusting for each of the following covariates separately and all covariates simultaneously using the methods described in Section 9.4.3:

- Wound location (medial malleolus, lateral malleolus, ankle flexure, posterior ankle, dorsum of foot, sole of foot, medial aspect of foot, lateral aspect of foot, big toe, 2nd through 5th toes [collapsed]; these locations have been re-examined and were recategorized based on the distribution and clinical considerations prior to database lock. Data will be summarized as weight bearing (plantar foot surface), and not weight-bearing (non-plantar foot surface).
- Age (\leq median and > median)
- Baseline wound area (≤ median and > median)

5. **DEFINITIONS**

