5.3.2. Definitions of Efficacy Endpoints

Complete Wound Closure

Defined as skin 100% re-epithelization without drainage or dressing at any time during the study. Complete wound closure will be assessed by the investigator at the sites and 100% reconciled with the ARANZ data, when possible. The primary analysis will be based on the eCRF page "Photography and Measurement of Ulcer in Target Leg".

Wound Volume, Wound Perimeter, Wound Area, and Wound Depth

The target wound's volume, perimeter, area, and depth will be measured using ARANZ Silhouette products at baseline and every scheduled post-baseline visit until wound closure.

Formation of New Foot Ulcer

Defined as a newly formed non-healing or poorly healing full-thickness wound, below the ankle on the target foot; these will be identified solely based the AE data provided by the site. The AE verbatim term will be scanned for the text "ULCER" and for "LEFT" vs. "RIGHT". The side will be matched with the target limb side from the eCRF and, if no information on site is present, it will be assumed that the new ulcer is on the target limb.

Major amputation

Defined as an amputation of the lower extremity above the ankle; these will be identified based on a blinded review of the AE data. The affected leg identified in the verbatim term on the AE electronic case report form (eCRF) and target foot noted on Physical Exam eCRF will be used to determine if the major amputation was in the target limb. These amputations will be noted in the clinical study report (CSR).

Minor amputation

Defined as an amputation of a foot or any parts of a foot such as toes; these will be identified based on a blinded review of the AE data. The affected leg identified in the verbatim term on the AE eCRF and target foot noted on Physical Exam eCRF will be used to determine if the minor amputation was in the target limb. These amputations will be noted in the CSR.

Cardiff Wound Impact Questionnaire (CWIQ)

The CWIQ is a patient-reported outcome measure designed to assess the impact of leg and diabetic foot ulcers on patient health-related quality of life (HRQoL). There are 3 domains/subscales:

- well-being (7 items, graded on a 5-point scale [1 = strongly disagree to 5 = strongly agree])
- physical symptoms and daily living (24 items, graded on a 5-point scale [1 = not at all to 5 = always])

• social life (14 items, graded on a 5-point scale [1 = not at all/not applicable to 5 = very])

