9. STATISTICAL METHODS

9.1. General Principles of Data Analyses

The primary analyses of the efficacy endpoints (Sections 9.4.1.1, 9.4.4) will be based on the ITT population. Additional sensitivity analyses for the primary efficacy endpoint, utilizing other populations and/or different ways of handling missing data, will be performed to further assess the effects of the treatment (Section 9.4.1.2). Supportive subgroup and covariate-adjusted analyses of the primary efficacy endpoint in the ITT population are described in Sections 9.4.2 and 9.4.3, respectively. Analyses of the safety outcomes (Section 9.5) will be based on the safety population.

The statistical analyses will be reported using summary tables, figures and listings. Continuous variables will be summarized with means, standard deviations, medians, minimums, maximums, and number of non-missing observations for each treatment group. Other selected percentiles, such as the 25th percentile and 75th percentile, may be presented for parameters that are not normally distributed or are suspected of exhibiting that tendency. Categorical variables will be summarized by counts and the percentage of subjects in corresponding categories. All data collected, including for subjects screened but not randomized, will be included in data listings.

All inferential statistical analyses will be performed with a two-sided confidence level of 95% or a two-sided significance level of 0.05.

All analyses and tabulations will be performed using SAS® Version 9.3 or higher on a PC platform.

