9.3. Demographics and Baseline Characteristics

The following outcomes will be summarized by the standard methods for continuous and categorical variables described in Section 9.1.

The demographics include the following parameters:

- Age at informed consent
- Sex
- Race
- Ethnicity

The baseline characteristics include the following:

- Wound location
- Baseline wound volume
- Baseline ABI
- Baseline TBI
- Toe pressure categorized by assessment method (Doppler, PPG)

- TcPO₂ (collected at a subset of study centers)
- Baseline BMI
- Baseline HbA1c
- Vital signs: blood pressure, weight, BMI, heart rate, respiration rate, temperature
- Medical history categorized by MedDRA system organ class (SOC)
- 12-lead EKG Interpretation: Normal, Abnormal NCS, Abnormal CS
- Urine pregnancy test: Positive, Negative, and Not Applicable

These parameters will be summarized by treatment group for the ITT population and included in data listings. Other collected baseline characteristics will be listed only.

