9.4.1.1. Primary Analysis of the Primary Efficacy Endpoint

The primary analysis for the responder rate will be based on the ITT population.

Fisher's exact test will be used to compare the responder rate between the treatment groups. The 95% confidence interval of the responder rate of each treatment group will be derived using the binomial distribution and the 95% confidence interval of the responder rate difference will be calculated.

Subjects whose status of wound closure cannot be assessed at 4 months (e.g., due to earlier discontinuation from the study), will be considered non-responders.

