9.4.3. Analysis of Covariates

The logistic regression model with treatment and all covariates listed in Section 4.5 will be used to obtain the 2-sided 95% confidence intervals for the covariate-adjusted estimate of the treatment effect for the primary efficacy endpoint.

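### The supportive covariate-adjusted analysis of the primary endpoint splits age and baseline wound area at the median; continuous terms would serve it slightly better, and the primary test is untouched

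*SAP*

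**What the plan says.** SAP 4.5 (Planned Covariates) names three covariates: wound location, reduced to weight-bearing or not; age, split at the median; and "Baseline wound area (≤ median and > median)". It states the intention as "The primary efficacy endpoint will be analyzed by adjusting for each of the following covariates separately and all covariates simultaneously" and refers to 9.4.3 for the method. SAP 9.4.3 says "The logistic regression model with treatment and all covariates listed in Section 4.5 will be used" to obtain a 95% confidence interval for the adjusted treatment effect. It specifies no separate fits, no test and no continuous coding.

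Three other places bear on this:

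- **Status.** SAP 9.1 introduces these as "Supportive subgroup and covariate-adjusted analyses of the primary efficacy endpoint in the ITT population". The primary analysis in SAP 9.4.1.1 is unadjusted: "Fisher's exact test will be used to compare the responder rate between the treatment groups".
- **Data held.** SAP 5.3.2: "The target wound's volume, perimeter, area, and depth will be measured using ARANZ Silhouette products at baseline". For percent change in perimeter, area and depth, SAP 9.4.4.4 uses the matching baseline measurement as covariate and states no split.
- **Baseline table.** SAP 9.3 includes baseline wound volume but not area, and adds that "Other collected baseline characteristics will be listed only".

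**The concern.** Protocol 3.3.1 admits ulcers from 0.5 to 15 cm², a 30-fold range (15 / 0.5). A median split gives every ulcer in the same half the same covariate value. If size predicts healing smoothly, the model discards the gradient within each half and adjusts only for the arms' shares above and below the median.

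This matters more in a small trial. SAP 1 gives enrolment by protocol version as 7, 5, 16 and 16, which sums to 44, and SAP 10 records that the study stopped early. The randomisation text in Protocol 3.2 and 3.4.7 mentions no stratification by ulcer size, so some chance imbalance is to be expected. The adjusted model is one of the few places where the plan takes wound size into account for the primary endpoint. The other is the Cochran–Mantel–Haenszel test in SAP 9.4.2, which uses the same split. What is at stake is how useful that supportive estimate is, not the trial's main result.

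**Working it through.** **Inputs from the documents.** Planned 200 v 100, two-sided alpha 0.05, closure rates 50–60% v 20–30% (SAP 6); enrolment 7 + 5 + 16 + 16 = 44 (SAP 1).

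**Assumed, because the documents do not give them.** Arms of 29 and 15 (about 2:1), and the strength of age and area as predictors, varied below.

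**1. The plan's own power figure.** Lowest row of SAP Table 4: 50% v 30%, power 0.898. With a continuity-corrected normal approximation:

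- difference: 0.20 − (1/200 + 1/100)/2 = 0.1925
- pooled rate: (100 + 30)/300 = 0.4333
- SE under the null: √(0.4333 × 0.5667 × 0.015) = 0.0607
- SE under the alternative: √(0.25/200 + 0.21/100) = 0.0579
- z = (0.1925 − 1.96 × 0.0607)/0.0579 = 1.27, so power is 0.898

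Exact enumeration of Fisher's test gives 0.918. All nine rows reproduce within 2 points. At 29:15 the exact Fisher power is 0.165 (50% v 30%), 0.409 (50% v 20%) and 0.638 (60% v 20%).

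**2. Likely imbalance.** The SD of the between-arm difference in a standardised covariate is √(1/29 + 1/15) = 0.32. The chance of a difference beyond 0.3 SD is about 35%, and beyond 0.5 SD about 12%.

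**3. Information about the covariate kept by a median split.** For a normal covariate the squared correlation with its own split is 2/π = 0.64. It is 0.75 for a uniform one. Under an assumed log-normal truncated to 0.5–15 cm², it is 0.68 for log area and 0.50 for raw area.

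**4. Power of the adjusted model, 29:15, closure 50% v 20%.** Logistic regression, Wald test, 4,000 simulated trials per row; Monte Carlo SE at most √(0.25/4000) = 0.8 points.

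| Log-odds per SD, age / area | Split | Continuous |
|---|---|---|
| 0 / 0 | 43.4% | 43.3% |
| −0.25 / −0.5 | 44.8% | 45.0% |
| −0.25 / −1.0 | 47.4% | 49.4% |
| −0.5 / −1.5 | 49.4% | 54.2% |

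Non-convergence was 3.2–6.0% with the split and 3.2–3.7% with continuous terms. Rejection under the null was 0.039–0.046 and 0.040–0.044. At 200:100 (50% v 30%) the cost of the split is 0.4–1.1 points.

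**5. A second set of simulations.** Treatment log-odds 1.5, age −0.3 per SD, 29:15, likelihood-ratio test, about 3,000 trials per setting. Interval widths use an assumed intercept of −1.1.

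| Log-area effect per SD | Power, split v continuous | Median width of log-odds CI, split v continuous |
|---|---|---|
| −0.7 | 0.57 v 0.57 | 3.16 v 3.24 |
| −1.0 | 0.52 v 0.55 | 3.23 v 3.39 |
| −1.5 | 0.44 v 0.49 | 3.39 v 3.72 |

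Null rejection was again alike (0.058–0.061 v 0.061–0.064). When the true area effect was a threshold instead, power was 0.57 v 0.57, 0.52 v 0.50 and 0.43 v 0.41 (split v continuous), so continuous coding gained nothing.

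**6. The estimate.** At −1.5 per SD the typical adjusted log-odds ratio was 1.50 with the split and 1.73 with continuous terms. The generating value was 1.5, so at 44 subjects the continuous fit overshoots, as maximum-likelihood logistic estimates tend to in small samples. The pull toward zero is therefore relative to the continuous fit. It shows against the true value at 200:100, where the generating value was 1.22 and the fits gave 1.08 (split) and 1.25 (continuous).

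**The case against.** The best defence is that little depends on this model. It is labelled supportive, SAP 8.4 recognises one primary analysis method, and no choice made in 9.4.3 can move the Fisher p-value. The coding also has a visible purpose: SAP 7.5 builds its subgroups from the 4.5 categories, so adjusted and subgroup results share one scheme. The gain depends on a linear effect and on prognostic strengths that the documents do not supply. All of this stands, and it limits the point to a refinement.

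A reader might infer more than the documents support:

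- **That the adjusted effect becomes less precise.** On the log-odds scale the continuous model's interval is wider. In logistic regression, adjusting for a stronger predictor raises both the conditional log-odds ratio and its standard error. The gain is in the ratio of the two.
- **That 36% of the information on treatment is lost.** The 0.64 describes the covariate, not the treatment effect.
- **That residual confounding undermines the comparison.** Randomisation protects it, and chance imbalance does not invalidate Fisher's test.
- **That imbalance in area would be hidden.** SAP 7.5 and 9.4.2 summarise the endpoint by arm within each half of area, so the denominators show the arm split at the median.
- **That 4.5 and 9.4.3 conflict in substance.** Section 4.5 states both kinds of fit and takes its method from 9.4.3. The latter's silence on separate fits is an editorial gap, and 9.4.2 already adjusts for each variable singly by Cochran–Mantel–Haenszel.

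**Conclusion.** The point holds as a modest improvement to a supportive analysis. The plan dichotomises two covariates that it holds as continuous values, while using measured baselines elsewhere. With 44 subjects the cost is about 0 to 5 points of power in the adjusted model. It is near zero if age and area predict weakly or if the area effect is a threshold, and reaches 5 points only with a strong, roughly linear log-area effect (−1.5 log-odds per SD). The adjusted log-odds ratio also comes out nearer zero than under continuous coding. These sizes rest on the assumed 29:15 split and on assumed prognostic effects.

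The primary test and its error rate are unaffected. Stopping at 44 is a far larger matter: Fisher power falls from the planned 0.898 or more to between 0.165 and 0.638 across the planning rates.

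**What to change.** - **SAP 4.5 and 9.4.3:** enter age and log(baseline wound area) as continuous covariates, with weight-bearing location as it is. Keep the median splits only for the subgroups in 7.5.
- **SAP 9.4.3 (tidying):** state that each covariate is fitted separately as well as jointly, as 4.5 intends.
- **SAP 9.3 (tidying):** add baseline wound area to the summary table.

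The cost is SAP wording and a few lines of programming, with no new data. The downside is the assumption that log-odds are linear in age and log area. The change should be made before the randomisation codes are released. If they already have been, report the continuous model beside the planned one and label it post hoc.
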